4.1.4.2 ASP7517 and Pembrolizumab Combination Therapy Arm DLTs

- Grade ≥ 3 non-hematological AE that does not resolve to \leq grade 2 within 72 hours of onset

- Grade ≥ 3 febrile neutropenia
 - Grade 3 febrile neutropenia is defined as absolute neutrophil count (ANC) $< 1000/\text{mm}^3$ with a single temperature of $> 38.3^\circ\text{C}$ (101°F) or a sustained temperature of $\geq 38^\circ\text{C}$ (100.4°F) for more than 1 hour.
 - Grade 4 febrile neutropenia is defined as ANC $< 1000/\text{mm}^3$ with a single temperature of $> 38.3^\circ\text{C}$ (101°F) or a sustained temperature of $\geq 38^\circ\text{C}$ (100.4°F) for more than 1 hour, with life-threatening consequences and urgent intervention indicated.
- Grade ≥ 3 thrombocytopenia accompanied by bleeding that requires transfusion or hospitalization
- Grade ≥ 3 anemia requiring transfusion
- Grade ≥ 2 pneumonitis
- Grade ≥ 2 encephalopathy, meningitis or motor or sensory neuropathy
- Confirmed Hy's law cases
- Aspartate aminotransferase (AST) or alanine aminotransferase (ALT) $> 5 \times$ upper limit of normal (ULN) in participants without liver metastases
- AST or ALT $> 8 \times$ ULN in participants with liver metastases
- Total bilirubin (TBL) $> 3 \times$ ULN (grade ≥ 3)
- Guillain-Barré syndrome or myasthenic syndrome/myasthenia gravis
- IRR that requires the infusion to be discontinued
- Prolonged delay (> 2 weeks) in initiating Cycle 2 due to treatment-related toxicity
- Any treatment-related toxicity that causes the participant to discontinue treatment during Cycle 1
- Grade 5 treatment-related toxicity

Participants experiencing a DLT will be discontinued from the study unless the participants are deriving clinical benefit from the study treatment in the opinion of the investigator; in those cases, after discussion with the sponsor, participants may be allowed to continue study treatment with ASP7517 upon resolution of the DLT event to \leq grade 1 or baseline.

Participants who are tolerating IP at a dose level that is being reviewed due to the occurrence of DLTs in another participant will not be automatically precluded from continued dosing during the safety review, and will be allowed to continue dosing for as long as tolerated unless directed otherwise as a result of the safety review by the DESC.

DLTs Requiring Discontinuation of Treatment

- If a study participant develops a grade 4 DLT after receiving Cycle 1, then the study participant should not receive Cycle 2 of the study product.
- If a study participant develops a grade ≥ 3 non-hematological AE that does not resolve to \leq grade 2 within 72 hours of onset, it should be considered a DLT and the study participant should not receive Cycle 2 of the study product.

If there is a delay in administration of Cycle 2 by > 4 weeks, it may result in discontinuation of Cycle 2 after discussion with the sponsor.

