4.1.3 ASP7517 and Pembrolizumab Combination Therapy Arm in Dose Escalation Phase 1 Cohort

In the combination treatment arm, ASP7517 will be given on Day 1 of each 28-day cycle for up to 6 doses in combination with pembrolizumab for up to 4 doses administered every 6 weeks, starting from Day 1 of Cycle 1. For combination treatment, a 400 mg pembrolizumab infusion will be administered first, followed by an ASP7517 infusion at least 1 hour after the completion of the pembrolizumab infusion. Following the first 2 cycles, participants who have not met any individual treatment discontinuation criteria and are receiving clinical benefit (defined as radiological response or SD, or reduction of disease-related symptoms) will continue further treatment with ASP7517 and pembrolizumab as decided by the investigator. Participants who achieve confirmed CR within the first 4 cycles will not receive further treatment with ASP7517 at Cycle 5 and Cycle 6 (end of Treatment period) and participants who achieve PR or SD after 4 doses may receive additional 2 doses of ASP7517 in combination with pembrolizumab.

Participants completing the Treatment period who enter the Observation Period with CR, PR or SD are allowed to continue on pembrolizumab alone up to a total of 17 doses for those participants who, in the opinion of the investigator, are continuing to derive clinical benefit.

Subsequent to the Treatment period, all participants, except those with iCPD, iUPD who are not clinically stable or have clinical disease progression per independent central review or local review will enter the Observation Period to monitor treatment response. Participants in the Combination Arm Observation Period will be followed for up to 78 weeks starting at EOT until iCPD (confirmed by independent central review or local review), initiation of a new anticancer therapy or meeting 1 of the Observation Period discontinuation criteria, whichever occurs first. If participant discontinues combination treatment of ASP7517 at any time prior to C5D15, then the participant should continue observation period up to a total of 96 weeks.

After discontinuation of IP, all participants will complete an EOT visit, along with 30-, 60- and 90-day safety follow-up visits from the last dose of IP or prior to the initiation of new anticancer treatment.

The initial dose escalation cohort of pembrolizumab combination with ASP7517 will use a starting dose of ASP7517 1×10^7 cells/dose.

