The decision to escalate to the next dose level (1×10^8 cells/dose) will be made based on the assessment of safety variables, including the occurrence of DLTs. A dose level of ASP7517 may be de-escalated to a lower dose level (1×10^6 cells/dose) based on the occurrence of

DLTs. Refer to [Section 10.1.5.1 Dose Escalation and Safety Committee] for details about the DESC.

All participants will be followed for survival, subsequent anticancer treatments and treatment outcomes following the conclusion of the Observation Period.

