7.1 Efficacy Assessments

Disease response and progression will be evaluated in this study using the RECIST v1.1 and iRECIST criteria as assessed by independent central review and investigator.

Tumor assessments will be performed at screening and at every 8 weeks (\pm 1 week) from C1D1 until confirmed disease progression by iRECIST (iCPD). Scans will be read on site and also submitted in digital format for independent central review. Procedures for independent imaging central review will be described in a separate imaging charter. The assessment will include tumor measurements for target lesions, non-target lesions, and assessment for any new lesions. An overall assessment will be characterized for time point evaluation.

Computed tomography (CT) or magnetic resonance imaging (MRI) scans are preferred for this study and to ensure comparability, the same technique (CT/MRI) used at screening should be utilized throughout the study. The same method should be employed and assessed by the same individual on each occasion, when possible. Imaging should include chest, abdomen and pelvis as well as any other anatomical region appropriate for the participant's disease.

Imaging should be done every 8 weeks from C1D1 regardless of treatment interruption or delays and through the follow-up period as applicable. Scans performed prior to informed consent as standard of care are acceptable as screening scans if done within 28 days prior to C1D1. If a biopsy of a target lesion is performed, the baseline scan should be repeated, if possible.

Confirmatory scans for CR or PR should be done at least 4 weeks after the date of the scan that CR or PR was first observed. Confirmatory scans for PD must occur at least 4 weeks after the date of the scan that PD was first observed but no longer than 8 weeks.

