The investigator will submit any updated SAE data to the sponsor within 24 hours of it being available.

Investigators are not obligated to actively seek AE or SAE after conclusion of the study participation. However, if the investigator learns of any SAE, including a death, at any time after a participant has been discharged from the study, and he/she considers the event to be reasonably related to the study IP or study participation, the investigator must promptly notify the sponsor.

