8.2 Discontinuation of Individual Participant(s) from Study

All participants who discontinue study treatment will remain in the study and must continue to be followed for protocol-specific follow-up procedures as outlined in the schedules of assessments [Table 3 to Table 6]. The only exception to this is when the participant specifically withdraws consent for any further contact with him/her or persons previously authorized by the participant to provide this information.

All participants who discontinue study treatment are to be followed for up to 12 months after their end of treatment, death or the final analysis, whichever occurs first per the schedules of assessments [Table 3 to Table 4].

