6.5.2 Adverse Events

For the purpose of safety assessments in this study, events recorded during the pre-investigational period will be classified as Baseline Signs and Symptoms. All adverse events (AE) recorded on treatment including within 30 days from the last study treatment and serious adverse events (SAEs) on treatment including within 90 days of the last study treatment will be summarized.

Summaries and listings of SAEs and Serious TEAEs include SAEs upgraded by the sponsor based on review of the Sponsor's list of Always Serious terms if any upgrade was done.

The coding dictionary for this study will be MedDRA v26.0. It will be used to summarize AEs by SOC and PT. AEs will be graded using National Cancer Institute's Common Terminology Criteria for AEs (NCI-CTCAE).

An overview table will include the following details by dose level, phase, tumor type, and overall:

- Number and percentage of participants with TEAEs
- Number and percentage of participants with IP related TEAEs
- Number and percentage of participants with TEAE leading to death
- Number and percentage of participants with IP-related TEAE leading to death
- Number and percentage of participants with serious TEAEs and Astellas upgraded serious TEAE
- Number and percentage of participants with serious IP related TEAEs and Astellas upgraded serious IP related TEAE
- Number and percentage of participants with TEAEs leading to permanent discontinuation of study IP
- Number and percentage of participants with IP related TEAEs leading to permanent discontinuation of study IP
- Number and percentage of participants with CTCAE grade 3 or higher TEAE
- Number and percentage of participants with CTCAE grade 3 or higher IP related TEAE

The number and percentage of participants with TEAEs, as classified by SOC and PT will be summarized by dose level, phase, tumor type, and overall. Summaries will be provided for:

- DLTs within the DLT observation period
- TEAEs
- Deaths
- IP related TEAEs
- Serious TEAEs and Astellas upgraded serious TEAE
- IP related serious TEAEs and IP related Astellas upgraded serious TEAE
- TEAEs leading to permanent discontinuation of study IP
- IP related TEAEs leading to permanent discontinuation of study IP
- CTCAE Grade 3 or higher TEAEs
- IP-related CTCAE Grade 3 or higher TEAEs
- TEAEs excluding serious adverse events that equal to or exceed a threshold of 5% in any dose level
- common TEAEs that equal to or exceed a threshold of 5% in any dose level

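### The combination-arm DLT rule discontinues participants from the study, while Sections 8.2 and 4.1.3 keep them in follow-up; the wording should say study treatment

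*Protocol*

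**What the plan says.** The rule appears twice in the protocol in the same words, each time after the combination-arm DLT list (Section 1.1, DLT Criteria; Section 4.1.4.2): "Participants experiencing a DLT will be discontinued from the study unless the participants are deriving clinical benefit". The exception rests on the investigator's opinion and, after discussion with the sponsor, allows ASP7517 to continue once the event has resolved. The monotherapy list in Section 4.1.4.1 has no such sentence.

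Other parts of the protocol say the opposite:

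- Section 8.2: "All participants who discontinue study treatment will remain in the study and must continue to be followed for protocol-specific follow-up procedures". It then adds: "The only exception to this is when the participant specifically withdraws consent for any further contact". A DLT is not named as an exception.
- Section 4.1.3, on the combination arm: "After discontinuation of IP, all participants will complete an EOT visit", followed by the 30-, 60- and 90-day safety visits. It also says: "All participants will be followed for survival, subsequent anticancer treatments and treatment outcomes following the conclusion of the Observation Period".
- Section 4.1.3 and footnote a of Table 4: a participant who stops ASP7517 before C5D15 continues the Observation Period for up to 96 weeks.
- Footnote t of Table 1 and footnote s of Table 2: when treatment is stopped early, an EOT visit takes place 7 days after the decision.
- Section 7.1: "Imaging should be done every 8 weeks from C1D1 regardless of treatment interruption or delays".

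**The concern.** The sentence tells a site what to do with a participant who has just had a DLT. Read as written, it ends study participation. The protocol elsewhere treats leaving treatment and leaving the study as different things (Sections 8.1 and 8.2), and nothing states which section prevails.

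Leaving the study has consequences that stopping treatment does not. Section 7.3.1 says: "Investigators are not obligated to actively seek AE or SAE after conclusion of the study participation". The SAP, Section 6.5.2, plans on a longer horizon: "serious adverse events (SAEs) on treatment including within 90 days of the last study treatment will be summarized". Appendix 10 warns that immune-related events may appear several months after the last pembrolizumab dose. A literal reading would therefore stop active surveillance in the participants who have already shown toxicity, and could remove them before any response assessment.

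**Working it through.** The plan gives no figure on this point to reproduce. The check compares the rule with the visit schedule.

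**Inputs.** C1D1 is Day 1, so study day = elapsed days + 1. The DLT window is 28 days from C1D1 (Section 4.1.4). Scans are every 8 weeks ± 1 week from C1D1 (Section 7.1). Safety visits are 30, 60 and 90 days after the last dose, each ± 3 days (Tables 3 and 4). Lentivirus samples are taken at C1D1, at 3 months or EOT (whichever is first), and at 6, 12 and 18 months (Table 5).

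**Latest usual time of a DLT.** The window closes on Day 28. One listed DLT, a delay of more than 2 weeks in starting Cycle 2, is reached later: C2D1 is planned for Day 29, and 29 + 14 = Day 43.

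**First response scan.** 56 ± 7 = 49 to 63 elapsed days, that is Days 50 to 64. Either kind of DLT comes before it. If removal waits for confirmation by the Dose Escalation and Safety Committee (Section 4.1.4), it could come after the scan.

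**Safety visits, for a participant dosed only on Day 1:**

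- 30-day visit: 27 to 33 elapsed, Days 28 to 34. It can just take place on Day 28, so it is usually but not necessarily lost.
- 60-day visit: 57 to 63 elapsed, Days 58 to 64. Lost.
- 90-day visit: 87 to 93 elapsed, Days 88 to 94. Lost.

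**SAE window in the SAP.** For a last dose on Day 1 the window ends on Day 1 + 90 = Day 91. With exit on Day x, the share without active collection is (91 − x)/90. For x = 28 it is 63/90 = 70%; for x = 43 it is 48/90 = 53%. The share depends entirely on the assumed exit day.

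**Lentivirus samples.** Three of the four post-baseline samples (6, 12 and 18 months) fall after exit.

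**Effect on the analysis sets and endpoints.** Without a post-baseline measurement the participant is outside the Response Analysis Set (Protocol 9.3), on which iORR is interpreted (9.4.2), and in phase 2 may be replaced at the sponsor's discretion (4.1.6.2). PFS and iPFS are censored at Day 1 if no death is known (SAP Tables 2 and 3), and OS at last contact (SAP 5.1.2.4).

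**How many could be affected.** The documents give no expected combination DLT rate. The nearest data, ASP7517 alone in another study, show 0 DLTs in 7 participants at the top dose (Section 4.3.1). The two-sided 95% upper limit is 1 − 0.025^(1/7) = 41%, which does not fix a combination rate. As an assumed range, take 5% up to 30%, the plan's target DLT rate:

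- Escalation, 12 participants: 12 × 0.05 = 0.6 to 12 × 0.30 = 3.6.
- Expansion, 232 participants: 232 × 0.05 = 11.6 to 232 × 0.30 = 69.6.

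These are ceilings on DLT cases. The clinical-benefit exception lowers the number removed, and the cohort sizes are planned totals in a study that the SAP (5.1.1) records as closed early.

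**The case against.** The strongest reply is that no careful site would read the sentence literally. Its own exception is about continuing study treatment, and the next heading in Section 4.1.4.2 concerns discontinuation of treatment. Section 8.2 is the section devoted to leaving the study, and it allows one exception only. The 96-week rule for early stoppers, the EOT footnotes and Table 3, which is titled for participants who end treatment early, all presuppose that such participants stay. This stands as evidence of intent, and it makes the harm conditional. It does not remove the conflict: each of these provisions disagrees with a sentence that is itself operative and is repeated in the synopsis.

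Much safety information also survives a literal reading. Serious and related events already known, and events of special interest, continue to be followed (Sections 7.3 and 7.3.3). Related SAEs that the investigator later learns of must be reported (7.3.1), as must all deaths up to 30 days after the last dose (7.3.5). This stands too, and it narrows the loss to scheduled visits and active seeking of new events. In addition, a participant who starts new anticancer therapy would end Observation Period scans under the correct wording as well (4.1.3).

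A reader might go further and infer that OS would be materially overstated because DLT cases are censored early. The documents do not support a figure. They give no combination DLT rate, no survival assumption and no excess hazard after a DLT; some of the relevant deaths are still captured as just described; and OS is a descriptive endpoint. On assumed inputs any effect is small, and it should not be reported as a finding.

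**Conclusion.** The inconsistency is real and appears in both places; severity is minor. It is a slip in an operative rule, and the documents give no sign that anyone chose to drop follow-up after a DLT.

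The consequences hold on two assumptions: that a site follows the sentence as written, and that the participant is not judged to be benefiting. Then the 60- and 90-day visits, usually the 30-day visit, active AE and SAE collection after exit, the 6-, 12- and 18-month lentivirus samples and the survival calls are lost. An exit before about Day 50 also costs the first scan and the place in the Response Analysis Set.

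Two further inferences should be resisted. Dose finding is not affected: participants with a DLT remain in the DLT Evaluation Analysis Set and, in escalation, are not replaced, so the MTD stands. Nor are all three safety visits necessarily lost, because the 30-day window opens on Day 28 after a Day 1 dose.

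**What to change.** In Sections 1.1 and 4.1.4.2, replace *discontinued from the study* with *discontinued from study treatment*, and add *and followed per Section 8.2*. Leave the clinical-benefit exception unchanged.

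The cost is one phrase in two places. No visit, scan, sample or call is added, since all are already scheduled for participants who stop treatment early, and no dosing decision changes.

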6.5 Dose Modification

Dose modifications of ASP7517 are not allowed at the individual participant level without prior consultation with the sponsor's medical monitor. Any participants who do not receive a subsequent dose within the scheduled time window in the schedules of assessments [[Table 1](#) and [Table 2](#)] can only resume treatment after discussion with the medical monitor. Any participant experiencing a grade 3 treatment-related AE after receiving a dose of ASP7517 may receive the subsequent scheduled dose of ASP7517 only after the observed grade 3 treatment-related AE has resolved to grade 1; the subsequent dose of ASP7517 may be reduced to a dose level deemed safe by the DESC. Further treatment reduction/withdrawal can be implemented after discussion with the medical monitor, including for any clinically significant AEs affecting vital organs (e.g., cardiac events).

Refer to the appendices and approved pembrolizumab package insert, summary of product characteristics monograph or local product information supplied by the manufacturer for the recommended treatment modifications for pembrolizumab.

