10.10 Appendix 10: Dose Modification and Toxicity Management for Immune-related AEs

AEs associated with pembrolizumab exposure may represent an immune-related response. These irAEs may occur shortly after the first dose or several months after the last dose of pembrolizumab treatment and may affect more than one body system simultaneously. Therefore, early recognition and initiation of treatment is critical to reduce complications. Based on existing clinical study data, most irAEs were reversible and could be managed with interruptions of pembrolizumab, administration of corticosteroids and/or other supportive care. For suspected irAEs, ensure adequate evaluation to confirm etiology or exclude other causes. Additional procedures or tests such as bronchoscopy, endoscopy, skin biopsy may be included as part of the evaluation. Dose modification and toxicity management guidelines for irAEs associated with pembrolizumab are provided in Table 17.

Based on the mechanism of action of ASP7517, immune-related adverse reactions (e.g., fever, headache, fatigue, hot flashes, diarrhea and muscular and joint pain) should be considered (see [Section 2.3.1.8 Other]) and managed as required per standard of care. In case of such events, ensure adequate evaluation to confirm etiology or exclude other causes. In addition, the study medical monitor should be contacted to discuss event monitoring, follow up and study treatment management.

Table 17 Dose Modification and Toxicity Management Guidelines for Immune-related Adverse Events Associated with Pembrolizumab

General instructions:

1. Severe and life-threatening immune-related adverse events (irAEs) should be treated with intravenous corticosteroids followed by oral steroids. Other immunosuppressive treatment should begin if the irAEs are not controlled by corticosteroids.
2. Pembrolizumab must be permanently discontinued if the irAE does not resolve or the corticosteroid dose is not ≤ 10 mg/day within 12 weeks of the last pembrolizumab treatment.
3. The corticosteroid taper should begin when the irAE is \leq Grade 1 and continue at least 4 weeks.
4. If pembrolizumab has been withheld, pembrolizumab may resume after the irAE decreased to \leq Grade 1 after corticosteroid taper.

Table continued on next page

irAEs	Toxicity grade (CTCAE v5.0)	Action with pembrolizumab	Corticosteroid and/or other therapies	Monitoring and follow-up

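### After a grade 3 non-hematological DLT that outlasts 72 hours and then resolves, one protocol rule bars Cycle 2 while two others conditionally allow further ASP7517, and no precedence is stated

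*Protocol*

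**What the plan says.** Three protocol rules bear on the next dose.

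- **The bar.** Section 4.1.4.2, under the heading "DLTs Requiring Discontinuation of Treatment", takes a grade 3 or higher non-hematological event that has not fallen to grade 2 or below within 72 hours and says that "it should be considered a DLT and the study participant should not receive Cycle 2 of the study product". The synopsis carries the same text twice: ahead of both arms' DLT lists, and again after the combination list.
- **The continuation clause.** Immediately before that heading, Section 4.1.4.2 says: "Participants experiencing a DLT will be discontinued from the study unless the participants are deriving clinical benefit from the study treatment", in the investigator's opinion. In that case, after discussion with the sponsor, "participants may be allowed to continue study treatment with ASP7517 upon resolution of the DLT event" to grade 1 or below, or to baseline. The synopsis repeats this after the combination list.
- **The dose-modification rule.** Under Section 6.5, any participant with a grade 3 treatment-related event "may receive the subsequent scheduled dose of ASP7517 only after the observed grade 3 treatment-related AE has resolved to grade 1", and "the subsequent dose of ASP7517 may be reduced to a dose level deemed safe by the DESC".

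Section 4.1.4.1, the body section on monotherapy DLTs, contains neither the bar nor the continuation clause. For pembrolizumab, the Table 17 instructions in Appendix 10 say: "If pembrolizumab has been withheld, pembrolizumab may resume after the irAE decreased to" grade 1 or below after the steroid taper.

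**The concern.** Whether a participant may be re-exposed after a DLT is an individual safety decision, so the protocol should give one answer. Here the answer depends on which section is consulted, and Section 6.5 is a natural place to look before giving the next dose.

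The analysis is affected too. Later-cycle adverse events, response, cumulative dose and (if the level is reduced) relative dose intensity in participants with a DLT would partly reflect the section that was followed. SAP Section 6.2.2 counts as deviations those participants who met withdrawal criteria but were not withdrawn. Whether a re-dosed participant belongs in that count depends on which rule governs.

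**Working it through.** No plan figure needs reproducing, so the check applies each rule to the same participant.

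**Do the rules overlap?** Section 4.1.4 requires a DLT to be related to the investigational product. A grade 3 DLT is therefore also a grade 3 treatment-related event, and Section 6.5 covers it.

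**Test cases.** Each is a related grade 3 non-hematological event in Cycle 1.

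| Case | Bar | Continuation clause | Section 6.5 |
|---|---|---|---|
| A. Above grade 2 at 72 h, later grade 1, benefit judged present | No Cycle 2 | ASP7517 may continue after sponsor discussion | Next dose may be given, same or reduced level |
| B. As A, no benefit | No Cycle 2 | Discontinued from the study | Next dose may be given |
| C. Above grade 2 at 72 h, returns to a grade 2 baseline, benefit present | No Cycle 2 | ASP7517 may continue after sponsor discussion | Not until grade 1 |
| D. Never reaches grade 1 or baseline | No Cycle 2 | No further dose | No further dose |
| E. Grade 2 or below within 72 h, then grade 1 | Does not apply | Applies only if a DLT on another criterion | Next dose may be given |

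Case C can arise because inclusion criterion 9 accepts prior-therapy events at grade 1 or baseline.

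The rules disagree in A, B and C. In C the two permissive rules also disagree with each other, because their resolution thresholds differ. In D no rule gives a dose. In E the bar is not triggered.

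**Does anything settle it?** None of the three rules cross-refers to another. Section 8.1 does not list a DLT among the mandatory reasons to stop treatment. SAP Sections 5.2.1.2 and 5.2.1.3 point back to protocol Section 4.1 for the DLT definition.

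**By arm.** In the body text, the bar and the continuation clause both sit in the combination section. For monotherapy the bar appears only in the synopsis, so the conflict there is mainly the synopsis against Section 6.5.

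**Size for one participant.** Under the bar: 1 dose. Under a permissive rule: up to 6 doses (the maximum in Section 4.1.1), a difference of up to 6 − 1 = 5. At an unchanged dose level, cumulative dose differs by up to a factor of 6 / 1 = 6.

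**Effect on dose finding.** The event counts as a DLT whichever rule is followed, and Section 4.1.5.2 says participants with a DLT are not replaced. The BOIN inputs and the MTD do not change.

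**The case against.** The strongest reply is that Section 4.1.4.2 states a general permission and then a specific exception. If the permission covered the events under "DLTs Requiring Discontinuation of Treatment", that heading would have little work to do. This is plausible and may be what was meant. The text does not say so, however, and it leaves Section 6.5 unreconciled.

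For Section 6.5, the reply is that it sets a minimum condition for re-dosing in any cycle and does not lift the DLT rules. That is also a fair reading, but again unstated, since the section covers any participant with a related grade 3 event.

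Oversight limits the risk. The DESC confirms DLTs, the continuation clause needs sponsor discussion, and Section 6.5 requires medical-monitor contact for a dose modification or a dose outside its window. A same-level, in-window dose under Section 6.5 carries no such express requirement.

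A reader might also infer four stronger points that the documents do not support:

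- **That 0.30 × 12 = 3.6, or 3 to 4 participants per arm, face the conflict.** The 0.30 is the BOIN target, not an expected rate, and many DLT criteria are of other kinds. Section 2.3.1 reports no DLTs in the first-in-human study.
- **That benefit cannot be judged before the first scan.** Section 4.1.3 defines benefit to include reduction of disease-related symptoms.
- **That grade 2 pneumonitis, a combination-arm DLT, necessarily takes the participant off study while Table 17 allows pembrolizumab to resume.** The continuation clause has a clinical-benefit exception, and Table 17 is permissive. What remains is that the clause names ASP7517 only and does not say how it relates to pembrolizumab.
- **That the MTD is compromised.** The DLT count is the same either way.

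**Conclusion.** The inconsistency is real and narrow. For a related grade 3 non-hematological event in Cycle 1 that is above grade 2 at 72 hours and later resolves, the protocol both bars Cycle 2 and conditionally permits further ASP7517. It gives no order of precedence and uses two resolution thresholds. An affected participant may receive 1 dose or up to 6. The number of such participants cannot be derived from the documents.

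This rests on reading the rules as written, without an unstated hierarchy, and on the participant meeting the conditions of at least one permissive rule. It takes no view on which clinical rule is right. The point still merits correction because it governs re-exposure after toxicity and can be resolved by wording alone.

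**What to change.** Reconcile the synopsis DLT text, Section 4.1.4.2 (the continuation clause and the list under its discontinuation heading) and Section 6.5 into one post-DLT treatment rule, stated for both arms and carried into Section 4.1.4.1. The rule should say:

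- which provision takes precedence;
- the single resolution threshold;
- whether Section 6.5, including its reduced-dose option, applies to DLTs;
- how the rule relates to pembrolizumab and Table 17.

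The sponsor's clinical team and the DESC choose the content. The cost is amendment wording, with no added participants or procedures.

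SAP Section 5.1.1 records early closure, so an amendment may have little prospective effect. If dosing has ended, the CSR should state which rule was applied and list each participant re-dosed after a DLT.
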